2.3. Aim

The primary aim of the study is to assess mortality, CV events and the rate of vascular and metabolic comorbidities potentially linked to cortisol excess (hypertension, diabetes, dyslipidemia, obesity) in patients with adrenal incidentalomas and calculate HRs for patient groups stratified by cortisol values following the 1-mg overnight dexamethasone test.

Two types of CV events are differentiated:

- ‘major CV events’: clinically symptomatic myocardial infarction or stroke followed by hospitalization, or CV-related death.
- ‘minor CV events’: any other type of myocardial infarction and therapeutic procedures for coronary heart disease (PTCA, surgical bypass), any stroke, transient ischemic attack, heart failure, deep vein thrombosis, pulmonary embolism.

CV events are optimally registered by hospital medical records reporting one (or more) of the followings: acute myocardial infarction and related therapeutic procedures (PTCA, surgical bypass), stroke, TIA, heart failure, deep vein thrombosis, pulmonary embolism, sudden death, or death from cardiovascular cause.

However, it will be allowed to obtain data with telephonic interview using a structured questionnaire aimed to recognize the presence of the above-mentioned comorbidities and the occurrence of major CV events (clinically symptomatic myocardial infarction, stroke, death).

We will assess:

- Overall Survival (OS) as primary endpoint, defined as the time interval between the date of discovery of adrenal incidentaloma and the date of death from any cause, in patients stratified by different cortisol cut-offs.
- Event-free Survival (ES), defined as the time interval between the date of discovery of adrenal incidentaloma and the date of occurrence of a 'major' and/or 'minor' CV event, in patients stratified by different cortisol cut-offs.
- CV mortality, defined as death from any CV cause, in patients stratified by different cortisol cut-offs. Other causes of death will be specified, as well.

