2.4. Methods

Retrospective, multi-center study

CV events are optimally registered by hospital medical records or can be obtained with telephonic interview using a structured questionnaire aimed to recognize the presence of the above-mentioned comorbidities and the occurrence of CV events.

Statistical analysis:

CV event rates will be expressed as the number of events per 1000 person-years.

Kaplan-Meier analysis will be used to construct survival curves and compute risks. Cox regression will be used for time-to-event analysis, and hazard ratios (HRs) computed with accompanying 95% confidence intervals (95% CI). Analysis will be stratified according to post-dexamethasone cortisol levels with three pre-specified cutoffs: ≤ 50 nmol/L (1.8 μ g/dL), 51-138 nmol/L (1.9-5.0 μ g/dL) and > 138 nmol/L (> 5 μ g/dL). However, additional cutoffs might be analysed as well.

Depending on the level of comprehensive documentation of the patients' characteristics two cohorts will be separately analysed:

- Cohort A: all requested data are available
- Cohort B: patients with missing data, but the following data are available: date of diagnosis the adrenal incidentaloma, result of 1mg DST, and survival status (or date of death).

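### Kaplan-Meier is the only method named for computing risks; if applied to event-free survival and CV mortality it overstates absolute CV risk, because non-CV deaths would be censored

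*Combined protocol and SAP*

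**What the plan says.** The statistical analysis part of section 2.4 (Methods) names three outputs: CV event rates per 1000 person-years, Cox hazard ratios with 95% confidence intervals, and risks. For the last it says "Kaplan-Meier analysis will be used to construct survival curves and compute risks". That sentence names no endpoint. The documents give no censoring rule and do not mention competing risks, cumulative incidence or cause-specific hazards.

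Section 2.3 (Aim) lists three endpoints:

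- Overall survival (OS), the primary endpoint: death from any cause.
- ES, which ends at "the date of occurrence of a 'major' and/or 'minor' CV event". The only death within a major event is CV-related: "clinically symptomatic myocardial infarction or stroke followed by hospitalization, or CV-related death". The list of events taken from hospital records is consistent with this, its fatal entries being "sudden death, or death from cardiovascular cause".
- "CV mortality, defined as death from any CV cause, in patients stratified by different cortisol cut-offs". The plan adds "Other causes of death will be specified, as well", but gives those other deaths no role in the analysis.

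Section 2.5 requires at least 36 months of follow-up and moved the earliest imaging date back to 1 January 1996 to lengthen follow-up. Section 2.8 sets data acquisition to close at the end of November 2018.

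**The concern.** A patient who dies of a non-CV cause can no longer have a first CV event or a CV death. Kaplan-Meier has no place for such a patient except as censored, which treats the later CV risk as still open. The result, 1-KM, is the CV risk in a hypothetical population where nobody dies of anything else. It exceeds the proportion of real patients who will have the event, and the gap widens with follow-up and with non-CV mortality.

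Longer follow-up is what the change of start date was meant to achieve: 1 January 1996 to the end of November 2018 is about 22.9 years at most. At stake are the absolute CV risks by cortisol group. If non-CV mortality differs between the groups, the overstatement differs too, and comparisons of absolute risk between groups are distorted.

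**Working it through.** The plan states no event rate, absolute risk or sample size, so there is no figure of its own to reproduce. The check uses assumed constant hazards.

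**Inputs**

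- *a*, CV hazard: 10 per 1000 person-years (0.01). Assumption.
- *b*, non-CV death hazard: 10 to 20 per 1000 person-years (0.01 to 0.02), with 40 as a stress value. Assumption.
- No deaths in years 0 to 3: one reading of the 36-month rule in section 2.5.
- Horizons *t* of 10 and 15 years, within the maximum of about 22.9 years.

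**Formulas**

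- Kaplan-Meier complement: 1-KM = 1 − exp(−*at*).
- True cumulative incidence without the 36-month reading: F(*a*,*b*,*t*) = *a*/(*a*+*b*) × [1 − exp(−(*a*+*b*)*t*)].
- ES with no deaths in years 0 to 3 and non-fatal CV events possible from time 0: true risk = 1 − exp(−3*a*) + exp(−3*a*) × F(*a*,*b*,*t*−3). 1-KM is unchanged.
- CV mortality with no deaths in years 0 to 3: replace *t* by *t*−3 in the first two formulas.

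**ES at 15 years, *b* = 0.02**

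- 1-KM = 1 − exp(−0.15) = 0.1393.
- F(0.01, 0.02, 12) = (1/3) × [1 − exp(−0.36)] = 0.1008.
- True = 0.0296 + 0.9704 × 0.1008 = 0.1274.

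**Results with no deaths in years 0 to 3, *a* = 0.01**

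| Endpoint, horizon | 1-KM | True, *b* = 0.01 | True, *b* = 0.02 |
|---|---|---|---|
| ES, 10 years | 9.5% | 9.3% | 9.1% |
| ES, 15 years | 13.9% | 13.3% | 12.7% |
| CV mortality, 10 years | 6.8% | 6.5% | 6.3% |
| CV mortality, 15 years | 11.3% | 10.7% | 10.1% |

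For ES the relative overstatement is about 2 to 5% at 10 years and 5 to 9% at 15 years.

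**Sensitivity**

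- Without the 36-month reading, the true 15-year risk is 13.0% (*b* = 0.01) or 12.1% (*b* = 0.02), against 13.9% by 1-KM.
- With *b* = 0.04 and the 36-month reading, the true 15-year ES risk is 11.7% against 13.9%.
- For two groups with *a* = 0.01 and 0.02, the 15-year ES difference by 1-KM is 25.9 − 13.9 = 12.0 points. With the 36-month reading the true difference is 11.0 points if *b* = 0.02 in both (23.8 − 12.7, from unrounded values), or 9.2 points if *b* doubles to 0.04 in the higher-risk group (21.9 − 12.7).

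**Check on the estimators.** A simulation of 200,000 patients with *a* = 0.01, *b* = 0.02, uniform censoring between 3 and 22 years and no 36-month restriction gave 9.50% by 1-KM against 8.62% by Aalen-Johansen at 10 years, and 17.93% against 14.87% at 20 years.

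The ES formula with the 36-month reading is an approximation. It keeps the full CV hazard in years 0 to 3, although part of that hazard is CV death, which the same reading rules out.

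**The case against.** **The target is inferred.** The Kaplan-Meier sentence names no endpoint. It could be meant for OS, where the method is right, and CV events have their own absolute measure in the person-year rate. This stands as a limit: the point is conditional on Kaplan-Meier being used for ES or CV mortality. It does not remove the point, because section 2.4 covers all three endpoints and offers no other way to compute a risk.

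**The main outputs are unaffected.** The stated aim is hazard ratios by cortisol group, and no risk difference or 15-year risk is promised. This also stands. A reader might infer that the mortality conclusions or the hazard ratios are biased. The documents do not support that: OS counts every death, rates remain valid as rates, and Cox models that censor at non-CV death give valid cause-specific hazard ratios.

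**The name event-free survival might suggest that all deaths count.** The definition does not say so; only CV-related death is included.

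**The size is assumed.** A reader might infer a large bias: a CV hazard of 5 and a non-CV death hazard of 40 per 1000, followed for 20 years without the 36-month reading, give a relative overstatement of 44%. Nothing in the documents supports those rates. The absolute gap there is only 2.9 points (9.5% against 6.6%), 20 years is reachable only for masses found in 1996 to 1998, and excluding active malignancy removes one source of non-CV death.

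**Telephone ascertainment is a different problem.** The interview is to identify "the occurrence of major CV events (clinically symptomatic myocardial infarction, stroke, death", with no cause attached to death. Read literally, non-CV deaths found that way would be ES events. It may only be shorthand for the definition given earlier in the section. Either way it concerns classification, which a change of estimator does not repair.

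**Conclusion.** The point holds in conditional form. If absolute risks or curves for ES and CV mortality are produced by the only risk method the plan names, they will be too high whenever non-CV deaths occur. Under the central assumptions the excess for ES is 0.2 to 0.4 percentage points at 10 years and 0.6 to 1.2 points at 15 years: small early, moderate at 15 years or more, and larger if non-CV mortality is higher. The direction follows from the endpoint definitions. The size rests on constant, assumed hazards and on reading the 36-month rule as no deaths in years 0 to 3. The change is worth making because the better estimator is cheap and uses cause-of-death information the plan already says it will specify.

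**What to change.** - Keep Kaplan-Meier for OS.
- For any absolute risk or curve of ES and CV mortality, report Aalen-Johansen cumulative incidence by cortisol group with non-CV death as the competing event, and state the censoring rule.
- Label the Cox hazard ratios for these two endpoints as cause-specific.
- Record each death as CV, non-CV or unknown.
- Run these analyses in the cohort with CV-event follow-up. Keep deaths of unknown cause in, and report bounds that count them all as CV and then all as non-CV. Do not exclude patients because the cause of death is unknown: dropping those deaths while keeping survivors selects on outcome. Cohort B needs only the date of diagnosis, "result of 1mg DST, and survival status (or date of death"), so its patients without CV-event data would not contribute here.
- Separately, reconcile the telephone wording on death with the CV-related death in the definition of major events.

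The cost is low: a little more analysis, no new follow-up, and one cause-of-death field. The minimum annotations in section 2.5 ask for the date of death but not its cause, so some centres may have to retrieve it.

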2.2. Scientific context

The natural history of adrenal incidentalomas is largely unknown. A number of recent studies have provided evidence for an increased rate of cardiovascular (CV) events and mortality in patients with adrenal incidentalomas and autonomous cortisol secretion. However, evidence comes from limited patient cohorts with rather short follow-up. Furthermore, a heterogeneous definition of autonomous cortisol secretion hampered to recognize which levels of functional autonomy are associated to increased morbidity and/or mortality.

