2.5. Requested clinical annotations (type, justification)

Inclusion criteria:

- Age ≥ 18 years
- Adrenal mass detected by sensitive imaging tests (CT or MRI) not done for suspected adrenal disease since 1-1-2000 (modified in Oct 2018 to 1-1-1996 to allow longer follow-up time)
- Imaging characteristics typical of adrenal adenoma: unenhanced or delayed enhanced CT, MRI with chemical shift and FDG-PET are all acceptable to secure this diagnosis.

- In the absence of appropriate imaging study, results of 12-month follow-up showing unchanged mass characteristics can be considered as surrogate criterion.
- Availability of 1-mg overnight dexamethasone test results done at diagnosis or during follow-up
- Follow-up duration of at least 36 months (from the date of diagnosing the adrenal mass the first time)
- Availability of follow-up data on living status and occurrence of CV events (telephone interview allowed to capture data)

Exclusion criteria:

- Presence of clinical features of overt Cushing's syndrome
- UFC $\geq 2 \times$ ULN
- ACTH-dependent Cushing syndrome
- Any active malignancy

Minimum clinical annotations:

- Date of birth, date of diagnosis
- Imaging characteristics (mass size, density on unenhanced CT (HU units), absolute or relative wash-out on delayed enhanced CT, results of MRI with chemical shift, results of FDG-PET, or imaging during follow-up > 12 months after initial imaging demonstrating unchanged tumor size)
- Serum cortisol following 1-mg DST, UFC, plasma ACTH (only serum cortisol after dexamethasone will be entered into the statistical model)
- Presence of obesity, hypertension, diabetes, dyslipidemia at initial diagnosis
- Information on prevalent CV events
- Date of last follow-up (date of death)
- Presence of obesity, hypertension, diabetes, dyslipidemia at last follow-up
- Information on incident CV events and date of first event

Minimum expected patient cohort per center: 50

Data acquisition via ENS@T registry

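### The primary overall-survival hazard ratio has no pre-specified confounder adjustment, and sex is not on the list of requested data (although the registry may hold it)

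*Combined protocol and SAP*

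**What the plan says.** Section 2.4 describes the design as "Retrospective, multi-center study" and plans Kaplan-Meier curves and Cox models: "Cox regression will be used for time-to-event analysis, and hazard ratios (HRs) computed with accompanying 95% confidence intervals (95% CI". The only grouping it names is the exposure: "Analysis will be stratified according to post-dexamethasone cortisol levels with three pre-specified cutoffs". Section 2.3 makes overall survival the primary endpoint and sets out to "calculate HRs for patient groups stratified by cortisol values following the 1-mg overnight dexamethasone test".

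Section 2.5 requests "Date of birth, date of diagnosis", so age at diagnosis can be derived. It also requests prevalent cardiovascular events and the presence of obesity, hypertension, diabetes and dyslipidemia at diagnosis. None of these is given a role in the model. Sex does not appear on the list. A parenthesis there, attached to the hormone measurements, says that post-dexamethasone cortisol alone goes into the statistical model.

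Two cohorts are to be analysed separately. The first is "Cohort A: all requested data are available". The second has incomplete data but must have "date of diagnosis the adrenal incidentaloma, result of 1mg DST, and survival status (or date of death". The plan does not say which of them carries the primary result.

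**The concern.** Stratifying by cortisol defines the comparison; it does not control confounding. Patients reach a cortisol group through their disease, and may also differ in age, sex or earlier cardiovascular disease, each of which can affect mortality. A crude hazard ratio mixes these differences with whatever cortisol contributes, so a cut-off could appear to carry excess mortality, or appear harmless, for other reasons.

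This bears directly on the motivation in section 2.2, where inconsistent definitions are said to have made it hard to "recognize which levels of functional autonomy are associated to increased morbidity and/or mortality". If covariates are instead added at the analysis stage, the primary result depends on a choice made after the data are seen. Several models fit the present text (crude; age only; age plus prior cardiovascular disease; all comorbidities), and they need not agree.

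**Working it through.** **1. Text check.** The plan states no sample size, event count, target hazard ratio or significance level, so there is no figure to reproduce. Reading every available section for a covariate, adjustment set, matching, weighting, centre term or selection rule finds none. What each data item could support:

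| Item | Requested in 2.5 | In Cohort B minimum (2.4) | Stated role in the Cox model |
|---|---|---|---|
| Post-dexamethasone cortisol | yes | yes | exposure |
| Date of birth (age) | yes | no | none |
| Sex | not listed | no | none |
| Prevalent cardiovascular events | yes | no | none |
| Baseline comorbidities | yes | no | none |

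The inclusion criterion of 18 years or over establishes adult status, not age.

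**2. Illustration: age.** All inputs are assumed. Suppose cortisol has no effect, age is the only confounder, and log hazard rises by *b* per year. With a difference *d* in mean age between the > 138 and ≤ 50 nmol/L groups, and age similarly spread in both,

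crude HR ≈ exp(*b* × *d*).

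| *b* per year | *d* = −4 | −2 | 0 | +2 | +4 |
|---|---|---|---|---|---|
| 0.05 | 0.82 | 0.90 | 1.00 | 1.11 | 1.22 |
| 0.08 | 0.73 | 0.85 | 1.00 | 1.17 | 1.38 |
| 0.10 | 0.67 | 0.82 | 1.00 | 1.22 | 1.49 |

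For example, exp(0.10 × 4) = exp(0.40) = 1.49.

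A simulation under the same assumption of no cortisol effect (3,000 patients; groups of 50/40/10%; age SD 10 years; 10% deaths over 7 years; middle group at half the gap) gave crude hazard ratios close to these, and age-adjusted ones of 0.98 to 1.01. At a 4-year gap either way, the crude comparison reached p < 0.05 in 11 to 56% of data sets, against 3 to 6% after age adjustment. This restates the formula for three groups; it says nothing about the actual patients.

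**3. Illustration: sex.** Let *p1* and *p0* be the assumed shares of men in the two groups and *h* the male-to-female hazard ratio. The bias factor is approximately

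(1 + *p1*(*h* − 1)) / (1 + *p0*(*h* − 1)).

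With 50% against 35% men:
- *h* = 1.3: 1.15 / 1.105 = 1.04
- *h* = 2.0: 1.50 / 1.35 = 1.11

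The reverse imbalance gives 0.96 and 0.90.

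**4. Price of stratifying by centre.** Only the minimum of 50 patients per centre comes from the plan (section 2.5). With 3,000 patients, 50/40/10% groups and 5 to 10% deaths, all assumed, simulation gives a standard error for the > 138 against ≤ 50 comparison larger by about 3% at 50 patients per centre, 5% at 25, 9% at 15 and 14% at 10. If the cortisol mix also varies strongly between centres, the increase at 50 per centre is about 12 to 13%.

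**The case against.** The strongest reply is that the plan is silent rather than wrong. Date of birth, prevalent events and baseline comorbidities are requested, so adjustment is possible and perhaps intended. Section 2.7 asks only whether a relationship exists, and a crude hazard ratio does describe one. It stands that no stated figure is wrong and that covariates have not been ruled out. But collecting a variable does not specify a model, and section 2.2 asks for more than a crude association.

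On sex, the list in section 2.5 is headed as a minimum and the data come through the ENS@T registry, whose fields are not shown. A reader might infer that sex is not collected. The documents do not support that; they show only that it is not requested by name and so is not guaranteed.

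A reader might also take the parenthesis in section 2.5 as ordering an unadjusted model. In its place, beside UFC and ACTH, it is better read as choosing among hormone measures. Neither reading names a confounder.

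It is also tempting to confine an adjusted primary model to Cohort A, where the data are complete. That would be a poor choice. Cohort A requires every requested item, including UFC, ACTH and comorbidities at last follow-up. The last may be less complete in patients who died, so membership could depend on the primary outcome, and patients usable for an age- and sex-adjusted model would be discarded.

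**Conclusion.** The concern holds. The primary hazard ratio has no pre-specified adjustment in a non-randomised comparison, and executing section 2.4 literally gives a crude estimate. This is more than missing detail, because it concerns the effect estimate for the primary endpoint, and a choice made after the data are seen cannot be made pre-specified later.

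The size is unknown. Bias could go either way, and there would be none if all confounders were balanced. The illustrative values rest wholly on assumed age gaps, sex shares and hazard slopes. A reader might infer from them that the result will be biased upwards, or by a given amount; the documents give no baseline data by group and support neither inference.

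Age and sex form the minimum adjustment. Prior cardiovascular disease may also confound, so an age- and sex-adjusted estimate could still carry residual confounding; a pre-specified second model would show how far it matters. How, or whether, to account for centre is a matter of preference.

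**What to change.** **In section 2.4:**
- Name one primary overall-survival model: Cox regression on cortisol group, adjusted for age at diagnosis and sex. Fit it in all patients with the necessary dates (diagnosis, and death or last follow-up), dexamethasone test result, survival status, age and sex, from Cohort A or B. For this model the separate analysis of the two cohorts would no longer be primary.
- Pre-specify a second model adding prevalent cardiovascular events. It is kept second because this item is not guaranteed in Cohort B, and requiring it would remove patients from the primary model.
- Pre-specify a further model adding baseline obesity, hypertension, diabetes and dyslipidemia, labelled as possible mediators, since section 2.3 itself treats these as potentially linked to cortisol excess.
- Report the crude hazard ratio as descriptive.
- Optionally account for centre, by stratification or frailty, and say which in advance. The strata should be judged by the number of patients who actually enter the model.

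**In section 2.5:** request sex by name, and clarify that the parenthesis only keeps UFC and ACTH out of the model.

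**Cost:** a paragraph of wording, one data field to confirm or add, and a little more analysis. Patients lacking age or sex leave the primary model, so their number should be reported by cortisol group. Centre stratification, if chosen, costs about 3% in standard error at 50 patients per centre under the assumed inputs, and more with smaller strata or a cortisol mix that varies strongly between centres.

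### Cohorts A and B, split by data completeness, are to be analysed separately with no exemption for overall survival; the plan gives no combined OS analysis and no lead cohort

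*Combined protocol and SAP*

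**What the plan says.** Section 2.3 names "Overall Survival (OS) as primary endpoint", measured from discovery of the mass to death from any cause and compared across cortisol groups. It names no analysis population.

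Section 2.4 plans Kaplan-Meier curves and Cox hazard ratios (HRs) with 95% CIs. It then states that, depending on how fully patients are documented, "two cohorts will be separately analysed". The split is defined in this way:

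- The fully documented group is given as "Cohort A: all requested data are available".
- The remaining group, B, is made up of "patients with missing data, but the following data are available: date of diagnosis the adrenal incidentaloma, result of 1mg DST, and survival status", with date of death given as the alternative to survival status.

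Section 2.5 sets inclusion criteria for everyone, among them "Follow-up duration of at least 36 months" and "Availability of follow-up data on living status and occurrence of CV events (telephone interview allowed to capture data". The annotations it requests include date of birth, UFC, ACTH, comorbidities at diagnosis and again at last follow-up, the date of the first incident CV event, and the date of last follow-up or death. It adds that post-dexamethasone cortisol is the only one of the hormone measurements to enter the model.

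No section describes a combined A+B analysis, ranks the cohorts, or says how differing OS results would be read.

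**The concern.** A split by completeness can make sense for CV events or covariate-adjusted models, where Cohort B may lack the data. The sentence is not limited to those analyses, so it also covers the primary endpoint. For OS, Cohort B already holds nearly everything needed, and dividing the deaths between two analyses costs precision. It also leaves two primary estimates with no rule for which one counts, so the choice could be made after the results are known.

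The criterion itself is also poorly suited to OS. Read literally, a patient who lacks only UFC or ACTH leaves Cohort A, although neither enters the OS model. Completeness also depends on last-follow-up comorbidities and the date of a first event, which are known only after time zero. If recording of those items were related to death, each cohort would be a selected sample for mortality.

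**Working it through.** **1. What OS needs, set against what Cohort B must have.**

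| Item for OS by cortisol group | Cohort B list (2.4) | Requested in 2.5 |
|---|---|---|
| Date of diagnosis | yes | yes |
| DST cortisol | yes | yes |
| Vital status | yes | yes |
| Date of death or last follow-up | not guaranteed: survival status or date of death | yes |
| Date of birth (for age) | not listed | yes |

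OS is therefore estimable in Cohort B for patients who have the dates. The 36-month criterion implies a known minimum follow-up, but it does not guarantee a usable censoring date.

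**2. Precision.** The plan gives no total sample size, number of deaths, power or A/B split, so there is no figure to reproduce. With D deaths and a proportion p in one of two cortisol groups, Var(log HR) ≈ 1/[D·p(1−p)]. A cohort with share s of the deaths and the same p has variance 1/[sD·p(1−p)]. The ratio of CI widths on the log scale is 1/√s:

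- s = 0.9: 1/√0.9 = 1.05
- s = 0.7: 1/√0.7 = 1.20
- s = 0.5: 1/√0.5 = 1.41
- s = 0.3: 1/√0.3 = 1.83

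A 70/30 split thus gives one CI 20% wider and another 83% wider than the combined CI.

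**3. Two answers and no lead.** The cohorts share no patients. If the true HR is 1 in both, the chance that at least one of two 95% CIs excludes 1 is 1 − 0.95² = 0.0975, against 0.05 for a single analysis. This is for one contrast, and it matters only if a CI excluding 1 is read as a finding. The plan states no significance rule.

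**4. Which items can put a patient in B after time zero.** Section 2.5 requires CV-event occurrence for every patient, so among eligible patients that item cannot separate A from B. Last-follow-up comorbidities and the date of a first event can. Section 2.4 allows a "telephonic interview using a structured questionnaire aimed to recognize the presence of the above-mentioned comorbidities". A living patient can answer it; for a deceased patient someone else must.

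**5. What dependence on outcome would do (assumed inputs only).** Take true mortality of 15%, completeness of 70% in survivors and completeness c in the deceased.

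Mortality in A = 0.15c/(0.15c + 0.85×0.7); in B = 0.15(1−c)/(0.15(1−c) + 0.85×0.3).

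- c = 0.7: 15.0% in both, no distortion.
- c = 0.6: A 0.090/0.685 = 13.1%; B 0.060/0.315 = 19.0%.
- c = 0.8: A 0.120/0.715 = 16.8%; B 0.030/0.285 = 10.5%.

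For the HR, a simulation assumed a true HR of 1.40, 40% exposed, a baseline hazard of 0.0175 per year and follow-up uniform over 3 to 13 years. It gave these event-rate ratios:

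- Completeness depending on cortisol only (60% low, 80% high): 1.40 in both cohorts.
- On death only (70% alive, 50% dead): 1.41 in A and just under 1.38 in B.
- On death and cortisol jointly (alive 70%; dead 50% low, 60% high): 1.67 in A and 1.14 in B.

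Only the joint pattern moves the HR materially. The combined analysis returns 1.40 by construction, because every simulated patient belongs to A or B.

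**The case against.** The strongest reply is that this is an omission rather than a wrong choice. The sentence does not name OS and does not forbid pooling. It states a basis for the split, and Cohort B's short list looks designed to keep patients in the study for survival. Reporting a fully and a minimally documented cohort side by side is a defensible retrospective design. All of that is fair, and the fix keeps the side-by-side report. It does not supply a primary population, and separate analysis remains the only instruction given.

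Two stronger readings are tempting, and the documents support neither.

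- **That the OS results will be biased.** Nothing shows that completeness depends on death or cortisol. Hospital records are the preferred source for CV events, and section 2.3 lists death among the events the interview may capture, so informants other than the patient are contemplated. The deceased could be the better documented group.
- **That the cohorts will probably contradict each other.** With an assumed 300 deaths, 40% exposed and the same HR of 1.4 in both, exactly one CI excludes 1 in 50% (50/50 split of deaths) to 69% (90/10) of cases. With 400 deaths, 30% exposed, HR 2.0 and a 50/50 split, it is 1%. One CI excluding 1 while the other does not is mostly limited power, not conflicting estimates.

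There are alternatives. Naming Cohort A as lead would remove the ambiguity, but not the lost precision or the post-baseline criterion. Inverse-variance combination of the two log HRs would do nearly as well (1.39 to 1.41 in the simulated scenarios), but the plan does not state it.

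It also stands that a combined model without age would be a weak primary analysis of all-cause mortality, and that data requested are not always data available.

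**Conclusion.** The point holds as a prespecification and precision problem that should be corrected. As written, the primary endpoint is analysed twice, in cohorts defined partly by items irrelevant to OS and partly by items recorded after baseline, with no combined estimate and no lead.

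The loss of precision is 1/√s. This relies on the usual large-sample variance and the same cortisol mix in both cohorts. It is small if one cohort holds nearly all the deaths (5% at 90%) and substantial otherwise. The 9.75% is exact for two independent 95% CIs, but it describes a reading rule that the plan does not contain. Selection bias is possible but not demonstrated, and the figures for it only show what pattern would be needed.

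**What to change.** - Make the primary OS analysis one Cox model by cortisol group in all eligible patients, A and B combined, who have date of diagnosis, DST result, vital status and date of death or last follow-up. Adjust it for age at diagnosis, taken from date of birth.
- Keep Cohort A as the sensitivity or further covariate-adjusted analysis. Define completeness on baseline items that enter the model or establish eligibility, not on last-follow-up items. UFC and ACTH may stay for eligibility, given exclusions such as "ACTH-dependent Cushing syndrome".
- Report A and B side by side, with mortality by cortisol group and the number excluded for missing dates, so that any dependence of completeness on outcome or cortisol can be seen.
- Add date of last follow-up or death to Cohort B's minimum data. Reconcile that list with the section 2.5 inclusion criteria, which require CV-event data.

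The cost is mainly wording, since every item is already requested in section 2.5. The drawbacks are that eligibility is less fully documented in Cohort B, that adjustment beyond age is limited there, and that Cohort B patients without a usable date will drop out of the time-to-event analysis unless the date can be retrieved.
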